**Specific data points in the protocol, along with a rationale for each change, are summarized below:**

- Complete Cardiac Rehabilitation Visits ***–in-person visits conducted in align with care delivery.***
- 6 Month Final Visit – ***conduct by phone or video visit.***
- Quality of Life, Mood and Cognitive Functioning Questionnaires ***-Questionnaires that can be obtained by phone or video visit.***
- Blood Test ***–Obtain historical results from medical records so not to require an additional in-person visit.***
- 24 Hour Ambulatory Blood Pressure ***–Not obtained so not to require additional in-person visits. During all Cardiac Rehabilitation visits blood pressure, heart rate are being monitor.***
- Brain MRI (Magnetic Resonance Imaging) – ***To be obtained at Neuroscience Center Imaging Department --this is the Primary Endpoint for the study.***

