	Secondary-Benefit	
 
6-month rates of recurrent stroke, myocardial infarction, hospital readmission for a cardiovascular or cerebrovascular indication, silent stroke on MRI and death.
 
Beginning and end comparison of weight, BMI, blood pressure, and laboratory values
 
		
SUBJECT SELECTION				
Targeted Accrual	
For this study, we will enroll 17 eligible ischemic stroke patients. We will continue to recruit patients until the 17th patient is enrolled in CCR.
			

Inclusion Criteria
 
 
Age <math>\geq</math> 18 years
 
Patient has suffered an ischemic stroke
 
Patient should be ambulatory (non-disabling stroke) to be able to participate in the CCR exercise program
 
Patient is able to start cardiac rehabilitation within 3 months of stroke
 
				

Exclusion Criteria
 
 
No baseline (index admission for ischemic stroke) MRI completed
 
Life expectancy < 1-year
 
Presence of brain hemorrhage: intracerebral hemorrhage, subarachnoid hemorrhage, subdural hematoma, or epidural hematoma
 
Concurrent diagnosis of seizure disorder
 
Patient with moderate or severe neurologic deficits, limiting their ability to participate in the CCR exercise program
 
Cardiopulmonary conditions preventing the patient from participation, such as severe heart failure, severe aortic stenosis, and exercise-induced asthma
 
Patient with cognitive dysfunction impairing their ability to follow directions
 
Anticipated procedures such as carotid stenting, carotid endarterectomy, and intracranial aneurysm coiling
 
Patient unable to commit to the frequent visits of the CCR program
 
Participation in other interventional research (observational research is allowed)
 
Unable to have brain MRI
 
Non-English speaker
 
Pregnant women
 
				

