## 4. STUDY DESIGN

This study is a prospective feasibility study, which will consist of a single arm of ischemic stroke patients. Seventeen patients will be consented through rolling recruitment to participate in a 36-session CCR program over 12-week period at Regions Hospital Outpatient Cardiac Rehabilitation facility. Participants will join the existing cardiac rehabilitation program, and undergo the same types of exercise therapy and education as the cardiac patients, with slight modifications to the educational material to include brain pathology. The primary endpoint of the study is the successful completion of the study protocol, which consists of attending 75% of the CCR sessions, completing brain MRI and laboratory tests at the end of the study, and attending the end of study visit.

Baseline data will be collected while patients are admitted at Regions Hospital. If patients need more time to recover, baseline visits will take place at HealthPartners Neuroscience Center within 3 months from the time of stroke. CCR sessions will also begin within 3 months after the patient's admission for ischemic stroke. The research staff will conduct a 6-week phone call (6-weeks after beginning CCR) to determine if any adverse events (AE) or serious adverse events (SAE) have occurred and to obtain and updated medication list. The 3-month and 6-month clinic visits will take place at the Neuroscience Center and will be 3 months and 6 months from the date of the baseline visit. Patients will meet with [name] and the research staff. The patients' vitals will be taken and standard assessments (described below) will be performed, which are typically performed as standard of care. The 6-month clinic visit will also include laboratory tests and a MRI. 24-hour ambulatory blood pressure will be monitored and recorded at baseline and at 6-months. The chart below includes the visit schedule and data collection information.

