#### **6.5. Vital Signs**

Vital signs and O2 saturation will be recorded at visits 1, 3, and 4 and recorded prior to the MRI and blood draw. For within subject consistency, brachial artery pressure will be obtained in the routine fashion and the same arm will be used for all study measurements.

Blood pressure and heart rate will be measured after subject has been sitting quietly for a minimum of 5 minutes. Vitals signs and O2 saturation will be monitored by clinical staff during each visit of the study.

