## **7.2. Subject Withdrawal**

Subjects may withdraw from study at any time for any reason without penalty or be terminated from the study by the clinical investigator (see provisions for termination by study team.) The investigational team will document the reason(s) for withdrawal. In the event a subject chooses to withdraw from study before Visit 4, the safety procedures described in Section 6.2.4. will be collected within 14 days following subject's decision to withdraw. For all subjects who withdraw, all final safety assessments will be collected regardless of time elapsed since the previous visit. In addition to final visit, subjects who withdraw early will be contacted within 7 days by study staff via telephone to assess for the development of any new and/or ongoing AEs and concomitant medications. Efforts will be made to recruit subjects to replace any withdrawals so as to maintain an n=17.

Subject's participation may be terminated at the discretion of the investigator. Individuals may be withdrawn for the following reasons:

- Clinically significant adverse events
- Lost to follow-up
- Protocol violations
- Inability to tolerate study intervention
- Other

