## **9.2. Preliminary Analysis**

Descriptive statistics, such as mean and standard deviation (for continuous variables) and frequency (for categorical and binary variables) will be computed for all demographic variables. Population demographics will include age, gender, stroke type, labs, BMI, and others.

No imputation for missing data or adjustment for multiple comparisons will be done as they were deemed too conservative for this feasibility study. All statistical analyses will be performed in SAS 9.4 with  $p<0.05$  considered to be statistically significant.

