## **9.4. Secondary Analyses**

For the secondary analyses, we will explore the potential benefits of cardiac rehabilitation for stroke patients by describing the 6-month rates of recurrent stroke, myocardial infarction, hospital readmission for a cardiovascular or cerebrovascular indication, silent stroke on MRI and death. We will assess the individual and composite event rates by calculating the mean and 95% confidence interval. This will provide information to allow us to power a larger study.

Additionally, we plan to descriptively compare weight, BMI, blood pressure, and laboratory values at the beginning and end of the study. We will do this by calculating the mean and 95% confidence intervals for these values.

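### The beginning-to-end comparison in Section 9.4 reports means and CIs of the values, not the within-patient change with a paired interval

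*Combined protocol and SAP*

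**What the plan says.** The synopsis lists as a secondary outcome: "Beginning and end comparison of weight, BMI, blood pressure, and laboratory values". Section 9.4 calls the comparison descriptive and gives one sentence of method: "We will do this by calculating the mean and 95% confidence intervals for these values". It names no analysis set.

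Other parts of the document bear on who contributes a value at each time:

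- Section 9.2: "No imputation for missing data or adjustment for multiple comparisons will be done".
- Section 7.2: "Efforts will be made to recruit subjects to replace any withdrawals so as to maintain an n=17".
- Section 4: "24-hour ambulatory blood pressure will be monitored and recorded at baseline and at 6-months".
- COVID-19 amendment, which changes the 6-month visit for the final 8 subjects. On 24-hour blood pressure: "Not obtained so not to require additional in-person visits". On blood tests: "Obtain historical results from medical records so not to require an additional in-person visit". The visit itself moves to phone or video, while the MRI is still done on site.
- Section 6.5: vital signs and oxygen "saturation will be recorded at visits 1, 3, and 4 and recorded prior to the MRI and blood draw". Section 6.6 has weight measured at the same three visits.

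**The concern.** With one arm, the only contrast available for these measures is each patient against himself or herself. The data are collected in pairs, and Section 6.5 even requires the same arm for blood pressure throughout, but the analysis text does not use the pairing. Two consequences follow.

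First, a CI around the beginning mean and another around the end mean are each valid, but neither describes the uncertainty of the change. A reader cannot reconstruct it, because that needs the correlation or the SD of the change, and neither is to be reported.

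Second, nothing ties the two means to the same patients. With no imputation, possible replacement of withdrawals and an amended final visit for 8 subjects, the beginning mean may include patients who are absent from the end mean. The difference between the means then partly reflects who was measured. This is certain for 24-hour blood pressure. It is unresolved for clinic vitals and weight in the final 8, whose visit is remote but whose MRI is in person. Section 9.4 also refers only to blood pressure, although seated clinic and 24-hour readings are both collected.

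**Working it through.** **Plan's own figure.** The plan gives no precision figure for this comparison. Its only one is ±20.2% for the completion rate (Section 9.5). It reproduces as a Wald half-width at 13/17: 1.96 × √(0.7647 × 0.2353 / 17) = 20.2%. At exactly 75% the result is 20.6%. It has no bearing on the change in weight, blood pressure or labs.

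**Inputs from the documents.** n = 17 (Sections 4 and 9.5). The final 8 subjects have no 6-month 24-hour blood pressure (amendment rationale), so there are at most 17 − 8 = 9 pairs for that measure.

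**Assumptions.** The documents give neither SDs nor a beginning-end correlation r. I take equal SDs at both times, express everything in SD units, and show r = 0.3, 0.5, 0.7 and 0.9.

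**1. What 9.4 would produce: a separate CI at each time.** Half-width = t(n−1)/√n.

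- n = 17: 2.120/√17 = 0.514 SD
- n = 9: 2.306/√9 = 0.769 SD

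A reader who judges change by whether the intervals overlap needs means further apart than the sum of the half-widths:

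- 17 vs 17: 0.514 + 0.514 = 1.03 SD
- 17 vs 9: 0.514 + 0.769 = 1.28 SD

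**2. Difference of the two means, treated as independent samples.** Half-width = t(n1+n2−2) × √(1/n1 + 1/n2).

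- 17 vs 17: 2.037 × √(2/17) = 0.699 SD
- 17 vs 9: 2.064 × √(1/17 + 1/9) = 0.851 SD

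**3. Mean within-patient change.** Half-width = t(n−1) × √(2(1−r)/n). This is also the size of mean change at which the paired CI first excludes zero.

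| r | Paired, 17 pairs (SD) | Unpaired 17 vs 17 ÷ paired | Paired, 9 pairs (SD) | Unpaired 17 vs 9 ÷ paired |
|---|---|---|---|---|
| 0.3 | 0.608 | 1.15 | 0.910 | 0.94 |
| 0.5 | 0.514 | 1.36 | 0.769 | 1.11 |
| 0.7 | 0.398 | 1.75 | 0.595 | 1.43 |
| 0.9 | 0.230 | 3.04 | 0.344 | 2.48 |

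**4. Break-even.** Setting the paired half-width equal to the unpaired one gives r = 1 − (unpaired half-width)² × n / (2 t²), with n the number of pairs and t = t(n−1).

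- 17 pairs: 1 − 0.699² × 17/(2 × 2.120²) = 0.08
- 9 pairs against 17 vs 9: 1 − 0.851² × 9/(2 × 2.306²) = 0.39

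Below these correlations, pairing does not narrow the interval.

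**The case against.** **The stakes are low.** The comparison is secondary and labelled descriptive, in a 17-patient feasibility study whose primary outcome is completion. The remark in 9.4 about powering a larger study follows the event rates, not these measures. The paired data are collected, so nothing is lost for good. All this stands and limits the weight of the point. It does not supply an estimate of change, and a description of change needs one as much as a test does.

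**The comparators are not in the plan.** Section 9.4 proposes neither an independent-samples interval nor an overlap rule, and the 17-vs-9 interval treats as independent two groups that share patients. This is fair: those figures only illustrate how far a reader could go wrong with the planned output. The point that separate CIs leave the uncertainty of the change unknown does not depend on them.

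**The 9-pair case is narrow.** It applies to 24-hour blood pressure only, and those readings are missing for administrative reasons rather than because of outcome. Both are true, so selection is less worrying there than with drop-out. The two means would still come from different patients.

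**Some values may be recovered.** Section 7.2 has final safety procedures collected within 14 days of an early withdrawal, and Section 6.2.4 includes vital signs and labs. Chart labs for the final 8 still give an end value, and baseline labs are taken from records for everyone. These points reduce the number of missing pairs but do not create a paired analysis. For labs the remaining question is timing, not absence.

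**The wording might cover differences.** One could stretch 9.4 to include change scores, and a statistician might well pair anyway. The text does not say so.

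**Conclusion.** The point holds. No section defines a within-patient change, a paired interval or a complete-pair set for a comparison that is by design within patients. As written, up to 17 beginning values of 24-hour blood pressure could be set against at most 9 end values.

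The gain from pairing depends on the correlation. With 17 pairs it narrows the interval for the change at almost any positive correlation; with 9 pairs it does so only above about 0.39. These sizes rest on equal SDs and an assumed correlation. The argument about comparing the same patients holds at any correlation. This should be changed as an inexpensive improvement to a secondary analysis.

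**What to change.** Replace the method sentence in Section 9.4 with wording such as:

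> For each measure we will report the mean within-patient change (end minus beginning) with a paired 95% t-interval in patients who have both values, the number of pairs, and the beginning and end means in that same set. The same type of measurement will be used at both times: 24-hour with 24-hour, clinic with clinic.

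It would help to add the SD of the change, and to state whether values taken at early withdrawal count as end values and how old a chart laboratory result may be.

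The cost is this text and a paired procedure in place of separate summaries, with no new data or visits. The drawbacks are a visibly smaller n for some measures and, for 24-hour blood pressure at low correlation, an interval no narrower than the unpaired one.

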## **9.5. Study Power**

Our sample size is based on the capacity of the CCR course as deemed by the cardiac rehabilitation program. With a sample size of 17, we will be able to estimate a completion rate of 75% to within a 95% confidence interval of  $\pm 20.2\%$ .

# **10. STUDY CONDUCT CONSIDERATIONS**

## **10.1. Regulatory and Ethical Considerations**

The study will be conducted in accordance with GCP guidelines. Subject privacy requirements will be observed, as well as the fundamental concepts of the Declaration of Helsinki (e.g. IRB approval of the study, obtaining informed consent from all subjects and meeting all reporting requirements).

## **10.2. Quality Assurance**

In the event of a regulatory agency audit or inspection, the site will allow the auditor/inspector access to all records documented and facilities utilized in conducting the study. The site will also make accommodations (e.g. time, schedule) to discuss findings, concerns, and questions with auditor/inspector.

### **10.3. Study Closure**

Upon completion of all subject visits, data entry and analysis, the investigator will inform the local IRB of study closure.

### **10.4. Records Retention**

All site records will be maintained and stored in a safe and secure location for a minimum of 15 years post study completion.

### **10.5. Provision of Study Results and Information to Investigators**

The study results will be made available by the study statistician once the analysis is complete.

### **10.6. Data Management**

Data collection and reporting tools will be developed and stored internally (e.g. Case Report Forms and source documents [Paper/REDCap]). Data collected and stored electronically will remain confidential and secure (e.g. secured server and password protected files [REDCap]). Study binders will be stored in a locked file cabinet within a locked office. After the study is closed, all subject identifiers will be destroyed.

